#### G. Summary

Given these findings, the current protocol aims to expand on these findings, and determine if the efficacy of anti-tumor vaccination can be improved by combination with PD-1 blockade in patients with early recurrent disease, specifically in a population with minimal residual disease that should theoretically be more amenable to anti-tumor vaccination. This trial will also evaluate whether GM-CSF is required as a vaccine adjuvant when using this combination, and gather safety and PSA response data using nivolumab alone for two cycles in patients with this earlier stage of disease. The hypothesis to be tested is that vaccination with PD-1 blockade will elicit a greater magnitude of tumor-specific CD8+ T cells, and this will result in an objective anti-tumor effect as measured by PSA declines, possibly PSA complete responses that are durable, and absence of metastatic progression at two years in patients who experience substantial ( $\geq 50\%$ ) PSA declines. The ability to drive PSA to undetectable levels, possibly curing or significantly delaying the metastatic recurrence of prostate cancer prior to the need for androgen depriving therapies, would be a “game changing” advance in the therapy of this disease. This will be conducted as a pilot, multiple-institution safety and feasibility trial. Identification of PSA responses (defined as PSA decline  $\geq 50\%$ ), and complete responses (PSA decline to  $< 0.2$  ng/mL), and delays in the time to disease progression will serve as evidence of clinical activity be used for planning future confirmatory clinical trials.

**Figure 1: Changes in serum PSA – patients treated with pTVG-HP and pembrolizumab.** 26 patients were randomized to treatment with pTVG-HP delivered 6 times over 12 weeks either concurrently with pembrolizumab (blue, delivered 4 times over 12 weeks), or sequentially (red, DNA vaccination over 12 weeks followed by pembrolizumab treatment over subsequent 12 weeks). Shown is the greatest change in serum PSA from baseline ( $p=0.013$ , Fisher's exact test, for any PSA decrease with respect to treatment arm). Green asterisks indicate those individuals that developed immune response to the PAP target antigen.

### 3. Objectives

#### A. Primary Objectives

1. To evaluate the safety and tolerability of pTVG-HP DNA vaccine and nivolumab in patients with clinical stage D0/M0 prostate cancer
2. To determine the PSA complete response rate (PSA  $< 0.2$  ng/mL)

#### B. Secondary Objectives

1. To evaluate 2-year metastasis-free survival rate
2. To evaluate median radiographic progression-free survival
3. To evaluate changes in PSA doubling time or slope
4. To evaluate PSA response rate ( $\leq 50\%$  of baseline)
5. To determine whether GM-CSF is required as a vaccine adjuvant for pTVG-HP vaccine when used in combination with nivolumab

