g If not performed within 7 days of this visit

h 28 days +/- 7d after off-study date, if prior to week 48, otherwise this visit not required

i If not already collected within previous 60 days

j Only use GM-CSF adjuvant if serum PSA at week 4 (V3) is higher than that obtained at day 1 (V1).

k Can be +/- 14 days of this visit

l PSA values used for screening/eligibility should all be from same clinical laboratory; for day 1 and subsequent visits, all PSA values should be from same lab, but not necessarily from same lab as used for screening

m Physical exam to include vital signs and ECOG status

n Physical exam does not need to be repeated on Day 1 if obtained within 14 days prior to the visit

o PSA obtained at week 4 and used to determine whether GMCSF will be added can be obtained within 7 days of the visit

p Patients will be followed for adverse events for 90 days after the last dose of nivolumab

q NaF PET/CT within +/- 7 days of study visit, exceptions may be allowed with prior approval from the study PI. The same PET/CT scanner should be used for each individual subject.

r NaF PET/CT should NOT be done within 2 days of GM-CSF injection.

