We have further explored means to increase the immunogenicity of DNA vaccines in murine models, and found that DNA vaccination elicited PD-L1 expression in tumors as a result of tumor-specific T cells elicited with vaccination that secrete IFN $\gamma$ . Combining vaccination with anti-PD-1 or anti-PD-L1 antibody treatment resulted in a greater anti-tumor response and eradication of tumors in some animals [18]. We have recently identified that this also occurs following human immunization using cryopreserved blood samples collected from patients with advanced prostate cancer treated with pTVG-HP. Using *in vitro* and *trans vivo* methods, we found that immune responses to PAP were detected and/or augmented when combined with PD-1 blockade [19]. Moreover, we detected increased expression of PD-L1 on circulating tumor cells following DNA vaccination, and we found that higher expression correlated with the development of persistent antigen-specific IFN $\gamma$ -secreting T-cell immunity [19]. These data suggested that combining PD-1 blockade with pTVG-HP should elicit superior anti-tumor effects in patients. We have now completed accrual to the first part of a pilot clinical trial using pTVG-HP in combination with pembrolizumab, in patients with metastatic, castration-resistant prostate cancer (mCRPC, NCT02499835). In this trial, patients received both agents, together or in sequence, over a 12-to-24-week course. We identified that treatment elicited PAP-specific Th1-biased immunity in some patients, and anti-tumor responses as measured by declines in serum PSA, and objective radiographic tumor responses as measured by CT imaging, were only detected in individual receiving the combination of agents (not sequentially). These are encouraging findings, notably because PD-1 blockade with either nivolumab or pembrolizumab alone has not demonstrated single-agent clinical activity in patients with advanced prostate cancer in previous phase I trials

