Granulocyte-macrophage colony-stimulating factor (GM-CSF) has been studied extensively by many groups in animal and human models as a vaccine adjuvant [41]. GM-CSF is a known growth and differentiation factor for human dendritic cells [42, 43]. Dendritic cells are specialized antigen-presenting cells (APC) that are believed to be responsible for stimulating naïve T-cell responses and to be the best cells at augmenting secondary immune responses [44]. They are known to cross present antigens encoded by DNA vaccines and taken up by bystander cells [45]. The dermis is a site for skin dendritic cells (Langerhans' cells) that are important in initiating immune responses by migrating to draining lymph nodes after antigen exposure for presentation of antigen to T-cells [46]. In human studies, soluble GM-CSF has been used as a vaccine adjuvant for a hepatitis B vaccine. In this phase I study, doses of 20-80 µg GM-CSF were administered just prior to and at the same site as the hepatitis B protein vaccination. Of 81 subjects treated with GM-CSF, 15 developed anti-HBs after only 1 injection (10 had protective titers) while only 1 of 27 patients vaccinated without GM-CSF produced a weak and transient antibody response [47]. GM-CSF-expressing autologous cells have also been demonstrated in murine and human studies to be able to elicit immune responses to autologous antigens [48-50]. GM-CSF has also been demonstrated to be a potent adjuvant for plasmid DNA vaccines. Several groups have demonstrated in animal models that plasmid DNA encoding GM-CSF can enhance the immune response generated to a target antigen when co-immunized with plasmid DNA encoding the antigen [39, 51, 52]. We have previously used recombinant human GM-CSF as a vaccine adjuvant for DNA vaccines, however its use has been dispensable in preclinical murine and rat studies,

suggesting it may or may not be required as an adjuvant for human use. This is being more formally evaluated in a separate trial (NCT02411786). In the current trial, GM-CSF will be used as an adjuvant in patients without evidence of PSA decline, to determine whether it required as an adjuvant for the pTVG-HP vaccine when used in combination with nivolumab.

D. PD-1 blockade and cancer treatment

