## **6. Experimental Design**

This will be a single-arm, multiple-institution, two-stage phase II trial designed to evaluate the safety and effect of serial intradermal vaccinations of a DNA vaccine encoding PAP with or without rhGM-CSF, and co-administered with nivolumab, on serum PSA in patients with PSA-recurrent, non-metastatic, non-castrate prostate cancer. A total of 20-41 patients will be accrued, treated over a maximum of one year each, and followed for up to two years for evidence of radiographic progression. All subjects will be followed an additional 2 years after their last treatment for evidence of delayed adverse events. The treatment will be as follows:

Nivolumab 240 mg IV every two weeks x 6 beginning day 1, then every four weeks x 9 beginning week 12

pTVG-HP (100 µg) administered intradermally (i.d.) every two weeks x 6 beginning day 1, then every four weeks x 9 beginning week 12

rhGM-CSF (208 µg) administered intradermally (i.d.) every two weeks x 4 beginning week 4, then every four weeks x 9 beginning week 12 NOTE: Only administered to patients for whom serum PSA obtained week 4 > serum PSA obtained at day 1.

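### Secondary objective 5 promises to determine whether GM-CSF is required, but GM-CSF is assigned by the week-4 PSA rise in a single-arm trial with no analysis specified, so the objective should be restated as descriptive.

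*Combined protocol and SAP*

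**What the plan says.** The Synopsis, Section 3.B and Section 10.B all list as a secondary objective: "To determine whether GM-CSF is required as a vaccine adjuvant for pTVG-HP vaccine when used in combination with nivolumab". Section 2.G repeats the aim: "This trial will also evaluate whether GM-CSF is required as a vaccine adjuvant when using this combination".

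Section 6 gives the assignment rule for GM-CSF: "Only administered to patients for whom serum PSA obtained week 4 > serum PSA obtained at day 1". Study Calendar footnote j and the visit descriptions in Section 8 from week 4 onward give the same rule. Sections 6 and 10.A describe a single-arm trial. Vaccine and nivolumab are scheduled for everyone from day 1.

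Section 2.C presents the rule as the means of answering the question: "GM-CSF will be used as an adjuvant in patients without evidence of PSA decline, to determine whether it required as an adjuvant". The same paragraph says of the general adjuvant question: "This is being more formally evaluated in a separate trial (NCT02411786".

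Section 10.D(3) covers 2-year metastasis-free survival, radiographic progression-free survival and PSA doubling time. Section 10.D(4) tests immune change from baseline without splitting by GM-CSF. Neither gives a comparison, an estimand or a criterion for calling GM-CSF required. Section 10.D(1) promises a detailed SAP before analysis.

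**The concern.** The objective is causal, but the design offers no contrast that isolates GM-CSF.

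- **Users against non-users.** The groups are separated by whether PSA rose in the first four weeks. They differ on an early form of the outcome before GM-CSF has been given.
- **Before against after, in users.** Vaccine and nivolumab continue throughout, so any change belongs to all three agents and to time.
- **Patients near the cut-off.** A threshold rule allows a local comparison in principle. It is not planned, and with at most 41 patients it is not realistic.

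What is at stake is a conclusion about the adjuvant drawn from a contrast that favours non-users by construction. The harmful case is a GM-CSF that truly helps while the observed comparison says the opposite.

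**Working it through.** **Plan's own figures.** No sample size, power or margin is stated for objective 5. The stated design (21 then 41 patients, stop at one or fewer PSA CRs in 21, reject at 5 or more in 41) concerns PSA CR only. It reproduces: P(X1 ≥ 2 and X1 + X2 ≥ 5) is 0.046 at a 5% rate and 0.902 at 20%.

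**Inputs for the illustration.** From the documents: the week-4 rule, a 28-day interval, PSADT3-9 from weeks 12 to 36, and trial sizes of 21 or 41. Assumed, and not in the documents: within-patient PSA CV 5–15%, and doubling time (DT) log-normal with log SD 0.7 and median 6, 12 or 24 months.

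**Step 1: how the rule sorts patients.** With no treatment effect, the expected log-PSA rise over 28 days is μ = (ln 2 / DT) × 28/30.44. The difference of two readings has SD s = √2 × CV. Then P(no rise) = Φ(−μ/s). For DT 12 months and CV 10%: μ = 0.0578 × 0.920 = 0.0531, s = 0.1414, μ/s = 0.376, P(no rise) = 0.35. P(rise) is 0.999 to 0.842 at DT 3 and 0.646 to 0.550 at DT 24 (CV 5% to 15%). Fast growers become users; slower growers are more often non-users.

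**Step 2: the contrast when GM-CSF does nothing.** PSADT3-9 = ln 2 / median group slope, from 300,000 simulated patients per cell. The trial percentages count trials with at least 3 patients per group.

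| Median DT | CV | Users (months) | Non-users (months) | Non-users look slower, n = 41 |
|---|---|---|---|---|
| 6 | 5% | 5.5 | 11.3 | 99% |
| 6 | 10% | 5.3 | 8.5 | 95% |
| 6 | 15% | 5.2 | 7.4 | 89% |
| 12 | 5% | 10.5 | 17.0 | 96% |
| 12 | 10% | 10.3 | 13.8 | 84% |
| 12 | 15% | 10.2 | 12.5 | 74% |

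Repeat runs move these by a point or two, so the range is about 75–99%. At median 24 it falls to about 60–84%. With 21 patients and median 6–12 it is about 69–98%.

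**Step 3: the contrast when GM-CSF helps.** Let GM-CSF cut the users' slope by 20%, which divides their doubling time by 0.8. At CV 10%:

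- Median 6: 5.3/0.8 = 6.6 months in users, against 8.5 in non-users.
- Median 12: 10.3/0.8 = 12.9, against 13.7 (13.8 in the table; the difference is simulation error).

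Users still look worse although GM-CSF works. A 30% cut would give 5.3/0.7 = 7.6 (still below 8.5) and 10.3/0.7 = 14.7 (now above 13.7), so masking depends on the size of the effect.

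**Step 4: a second model.** Assume instead that 20% of patients respond to treatment (log-PSA slope lowered by 0.3–1.0 per month), median DT 3–12 months, log SD 0.6, and no GM-CSF effect. PSA declines of at least 50% then occur in 0–1% of users and 38–71% of non-users. The size changes with the model; the direction does not.

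**Step 5: what silence among non-users would mean.** In the Step 2 model, at median 6–12, non-users number about 2–8 of 21 or 4–16 of 41. The Wilson 95% upper limit for 0/n is z²/(n + z²), with z² = 3.84: 66% at n = 2, 49% at n = 4, 32% at n = 8, 19% at n = 16. No responses in such a group would not show that GM-CSF is required.

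**The case against.** **Nobody planned a user against non-user test.** Section 2.C describes add-on logic: begin without GM-CSF and add it where PSA has not fallen. Required is a necessity claim, and responses without GM-CSF can refute necessity. This stands, and it is why the fix keeps one-sided statements. It does not support the converse, and no criterion is written down.

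**If GM-CSF has no effect, concluding that it is not required is correct.** This stands too. A reader might infer from Step 2 alone that the design returns a false answer; the no-effect results show only a biased contrast. The false answer is the hidden benefit in Step 3.

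**A no-effect trial would not normally reach 41 patients.** Entry needs PSA of at least 2.0 ng/mL and rising, so PSA CRs below 0.2 would hardly occur and Section 10.C would stop the trial at 21. This is fair, and the 21-patient figures are given for that reason.

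**The assumed doubling times are narrow.** Eligibility sets no upper limit on PSADT. This is also fair: the bias shrinks at median 24. The visit and blood-draw windows, which let the triggering interval depart from 28 days, were not varied.

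**It is one secondary objective in a self-described pilot.** No decision rule or sample size rests on it, and a separate trial is named as the more formal evaluation. That lowers the priority but does not justify the word determine.

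**Conclusion.** The point holds. Objective 5 claims something that the assignment rule prevents the trial from delivering. A later SAP could add an analysis but could not undo assignment on an early value of the outcome. The direction of the bias follows from the rule; its size rests on the assumed CV and doubling-time distribution, which the documents do not give.

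Three stronger readings are not supported. The trial is not silent on GM-CSF: responses in patients who never received it are informative in one direction. The hiding of a benefit is possible rather than certain, as the 30% case at median 12 shows. The primary PSA CR analysis is not affected.

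This is a wording and analysis-plan point that should be corrected, at the lower end of that priority.

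**What to change.** 1. In the Synopsis, Section 3.B and Section 10.B, restate objective 5 as: *To describe PSA and PAP-specific immune outcomes in patients who do and do not receive GM-CSF under the week-4 rule.* Align Sections 2.C and 2.G.
2. Add to Section 10.D(3) the rates of PSA CR, PSA decline of at least 50%, and PAP-specific T-cell and IgG response in each group, with 95% confidence intervals. State that no between-group or before/after contrast is read as a GM-CSF effect.
3. Permit only these one-sided statements:
   - PAP-specific responses meeting the Section 9.B definitions in patients never given GM-CSF, or IgG responses in week-4 blood drawn before any GM-CSF, show that it is not indispensable for those responses. Week-4 blood alone cannot meet the T-cell definition, which needs two post-treatment detections.
   - PSA responses without GM-CSF show that the combination can produce a response without it. They do not credit the vaccine, because everyone receives nivolumab.
   - Absence of response in non-users does not show that GM-CSF is required.
4. Refer the formal question to the separate trial named in Section 2.C.
5. Separately, reconcile two wordings. Section 2.G says the trial will "gather safety and PSA response data using nivolumab alone for two cycles", while Sections 6 and 8.C schedule vaccine with nivolumab from day 1. Section 2.C ties GM-CSF to the absence of a decline, while footnote j and Sections 6 and 8 tie it to a rise; the two differ for an unchanged PSA.

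The cost of items 1–4 is a few lines of text and one short paragraph. The trial gives up a claim that it could not have supported; enrolment, treatment and the primary analysis are unchanged.

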#### Laboratory/Exploratory Biomarker Objectives:

1. To determine if antigen-specific T-cell and/or IgG responses are elicited with treatment

2. To determine if the development of PAP-specific T-cell immune responses are associated with PSA response (decline  $\geq 50\%$ )
3. To determine if antigen spread (the development of immune responses to other cancer-associated proteins) is associated with PSA response (decline  $\geq 50\%$ )
4. To determine if Quantitative Total Bone Imaging (QTBI) by NaF PET/CT can identify bone lesions in this patient population not detected by standard bone scintigraphy
5. To determine whether the presence of lesions detected by NaF PET/CT at baseline is associated with early disease progression (within 1 year) by standard radiographic imaging methods (CT and bone scintigraphy)
6. To determine if growth rates, and changes in growth rates, determined by NaF PET/CT are associated with PSA doubling time and changes in PSA doubling time

#### 4. Vaccine and Nivolumab Preparation

A. Anti-PD-1 monoclonal antibody (Nivolumab, Opdivo®)

Nivolumab (Opdivo®, Bristol Myers Squibb) is a human programmed death receptor-1 (PD-1)-blocking antibody indicated for the treatment of patients with multiple different types of cancer. While this agent is commercially available, its use is investigational under this protocol. A fixed dose will be used based on the approved dosing of 240 mg IV every 2 weeks for several malignancies. This dose will be used for all treatments, even during the period of monthly administrations, given that nivolumab is being used in combination rather than as a single-agent therapy. Nivolumab is supplied in 100 mg (10 mL of a 10mg/mL solution in a single-dose vial) quantities. For each administration, three 100-mg vials will be used to achieve the 240 mg fixed dose.

The most common adverse reactions (reported in  $\geq 20\%$  of patients) included fatigue, cough, nausea, pruritis, rash, decreased appetite, constipation, arthralgia, and diarrhea. Immune-mediated adverse reactions have also been observed, including immune-mediated pneumonitis, colitis, hepatitis, hypophysitis, nephritis, hyperthyroidism and hypothyroidism. The management of suspected adverse reactions is discussed in Section 7 below.

## B. Plasmid DNA vaccine

pTVG-HP pTVG4 vector containing cDNA for human PAP

The sequence of the pTVG-HP plasmid has been confirmed by standard DNA sequencing to confirm its identity. A bacterial strain was transformed with this plasmid and transferred to the National Gene Vector Laboratories (NGVL) manufacturing facility (Center for Biomedicine and Genetics, City of Hope/Beckman Research Institute, Duarte, CA) from which a master cell bank was prepared. This master cell bank was shipped in 2008 to the Waisman Clinical Biomanufacturing Facility (WCBF) at the University of Wisconsin. Several GMP-grade lots of

plasmid DNA have been prepared at the WCBF. The biological activity of each lot has been tested by production of PAP following transfection of reporter cells *in vitro*. Lots were also tested for appearance, plasmid homogeneity, DNA identity by restriction endonuclease evaluation, protein contamination, RNA contamination, genomic DNA contamination, sterility, endotoxin, and pH, and criteria for each of these have been established for future lot release. The vaccine will be supplied in single-use vials containing 0.6 mL 0.2 mg/mL pTVG-HP in phosphate-buffered saline. Vials will be stored at -80°C (or -20°C if further stability testing confirms that this is appropriate) until the day of use.

C. GM-CSF

GM-CSF (Leukine®, Sargramostim), will be obtained from Berlex Laboratories (Montville, NJ), or other commercial pharmaceutical vendors, and may be used as a vaccine adjuvant, provided without cost to subjects participating in this trial. GM-CSF, as described above, is a growth factor that supports the survival, clonal expansion and differentiation of hematopoietic progenitor cells including dendritic antigen presenting cells. In preliminary animal experiments and human clinical trials GM-CSF has been shown to be safe and serve as an effective adjuvant for the induction of antibody and T-cell responses to the immunized antigen [41, 64]. The use of GM-CSF is associated with little toxicity [42, 47, 65]. GM-CSF is a sterile, white, preservative-free, lyophilized powder supplied in 250 µg-dose vials.

Recombinant human GM-CSF (rhGM-CSF), when administered intravenously or subcutaneously is generally well tolerated at doses ranging from 50 to 500 µg/m^2/day. Severe toxic manifestations are extremely rare in patients treated with rhGM-CSF. Diarrhea, asthenia, rash and malaise were the only events observed in more than 5% of the rhGM-CSF group compared with the placebo group in phase III controlled studies of patients undergoing autologous bone marrow transplantation. In uncontrolled phase I/II studies for various indications, the adverse effects reported most frequently were fever, chills, nausea, vomiting, asthenia, headache and pain in the bones, chest, abdomen, joints, or muscles. Most of these systemic events reported with rhGM-CSF administration were mild to moderate in severity and rapidly reversed by the administration of analgesics or antipyretics. Other events reported infrequently were dyspnea, edema, local injection site reactions, and rash. Thrombosis and cardiac arrhythmia have also been reported, and there have been infrequent reports of tissue sloughing, leukemic progression, congestive heart failure, hepatomegaly, and intracranial bleeding; and isolated reports of Guillain-Barré syndrome and increased histiocytes. Neutropenia, although usually a pre-existing condition in the patients receiving rhGM-CSF, has been reported in association with administration. There was an increased frequency of severe thrombocytopenia in patients receiving concurrent chemotherapy and radiotherapy with GM-CSF. Eosinophilia and other blood abnormalities may occur.

There have been rare reports of 1) sequestration of granulocytes in the lungs with respiratory symptoms; 2) a syndrome characterized by respiratory distress, hypoxia, flushing, orthostatic hypotension, and partial loss of consciousness; 3) peripheral edema, pericardial or pleural effusions, and capillary leak of fluid; and 4) serious allergic or anaphylactic reactions.

Administration of rhGM-CSF may aggravate fluid retention in patients with pre-existent edema, capillary leak syndrome, or pleural or pericardial effusions. In some patients with pre-existing renal or hepatic dysfunction, elevation of the serum creatinine or bilirubin and hepatic enzymes

has occurred during the administration of rhGM-CSF. Dose reduction or interruption of rhGM-CSF administration has resulted in a decrease to pretreatment values. Occasional transient and reversible supraventricular arrhythmia has been reported in uncontrolled studies, particularly in patients with a previous history of cardiac arrhythmia.

Stimulation of marrow precursors with rhGM-CSF may result in a rapid rise in white blood cell count. Dosing should be stopped if the ANC exceeds 20,000/cm^3. rhGM-CSF may stimulate the growth of myeloid malignancies; therefore, caution must be exercised in its use in these malignancies or myelodysplastic syndromes.

Because GM-CSF will only be administered at most once every two weeks on the current protocol, most of these side effects are not anticipated. In previous vaccine studies using rhGM-CSF as an adjuvant in an identical fashion, local skin reactions consisting of erythema and induration have occurred in many patients. These resolved without need for treatment over a 2-3 week period for some, and over 2-3 days for most. Transient leukopenia (lasting only a couple of hours) has been observed in some patients, and resolved without treatment and without clinical sequelae [66]. Furthermore, the generation of a transient immune response to rhGM-CSF following its use as a vaccine adjuvant has been observed, however no clinical sequelae were noted, and the significance of this observation is not clear at present [65].

